
4 STUDY DESIGN

4.1 OVERALL DESIGN

The main objective of this study is to evaluate the efficacy of adding WET to a course of ketamine infusions in improving PTSD symptoms from baseline to 12 weeks from the start of WET, in individuals with chronic PTSD (Aim 1). Additional objectives are to evaluate whether ketamine-induced change in extinction learning, assessed with an online Extinction Learning Task, predicts PTSD symptom improvement (Aim 2) in participants with chronic PTSD. In order to accomplish these objectives, we will conduct an open-label trial of ketamine plus WET in individuals with chronic PTSD. Participants will start WET after completing the first four ketamine infusions. Participants will receive two additional ketamine infusions (for a total of six infusions), interwoven with five WET sessions.

Eligible participants will receive a total of six ketamine infusions (see Figure 1 and Methodological Details below), administered over 2 consecutive weeks,⁴⁹ and will also begin WET sessions. The first 2 WET sessions will be administered interleaved with the last 2 ketamine infusions, on different days. The last three sessions of WET will be administered during the week following the end of ketamine infusions.

The clinical trial primary outcome is change in PTSD symptom severity from baseline to 12 weeks from the start of WET, measured with the CAPS-5⁵⁰. Secondary outcomes include change in PTSD symptom severity from baseline to 6 weeks from the start of WET, and change in other outcome measures from baseline to 6 weeks, and baseline to 12 weeks. Patients whose improvement in PTSD symptoms is maintained after 12 weeks will complete monthly assessments up to 24 weeks from start of WET. A continuous clinical rater will administer the CAPS-5 and the MADRS for the primary and secondary outcome assessments.

Methodological Details

a. Screening Procedures (see 3.1 Schedule of Activities): Individuals will undergo informed consent procedures and study screening at the clinical site. If the COVID-19 pandemic remains a concern, these procedures will be conducted remotely, via a HIPAA-compliant telehealth platform (e.g., VSee, Doximity, HIPAA-Zoom). After signing the informed consent form, participants will complete a structured diagnostic interview with the SCID-5,⁵¹ the CAPS-5 to determine PTSD symptom severity,⁵⁰ the MADRS to determine depressive symptoms severity,^{52,53} the Wechsler Test of Adult Reading (WTAR),⁵⁴ and the Montreal Cognitive Assessment test (MoCA).⁵⁵ Please see **3.1 Schedule of Activities** for a complete list of scales to be completed by study participants at screening. All subjects will complete forms related to demographics, medical history, concomitant medications and treatment, and self-report measures including the Childhood Trauma Questionnaire (CTQ),⁵⁶ Traumatic Life Events Questionnaire (TLEQ),⁵⁷ PTSD Checklist for DSM-5 (PCL-5),⁵⁸ and Sheehan Disability Scale (SDS).⁵⁹ Participants will also undergo a medical evaluation, including medical history; physical examination by a nurse practitioner; documentation of height, weight and vital signs; comprehensive blood tests; and urinalysis, urine toxicology screen, and urine pregnancy test (in women of childbearing potential). After reviewing all information, the PI or other study psychiatrist will meet with each patient to review their psychiatric and medical history, and current medications and treatment, answer any questions the patient might have,

administer the Columbia Suicide Severity Rating Scale (C-SSRS)⁶⁰ and the CGI-S,⁶¹ document contraceptive use, and verify patient eligibility for the study. If a participant is taking any exclusionary psychotropic medication listed in the exclusion criteria, the prescribing psychiatrist or other prescribing physician must taper the participant off the medication, in consultation with the study PI or other study psychiatrist, if it is determined that the medication is of no clinical benefit to the individual.

b. Administration of ketamine infusions: Eligible participants will receive a total of six infusions, administered over two consecutive weeks. At each infusion, they will receive 0.5 mg/kg of racemic ketamine hydrochloride, and total dose no higher than 60 mg per infusion (regardless of body weight). All infusion procedures and monitoring will take place at the Icahn School of Medicine at Mount Sinai (ISMMS) Psychiatry Infusion Suite or Clinical Research Unite (CRU) using the existing Standard Operating Procedures that are in place for the administration of ketamine in research studies.

c. Assessment of response to ketamine: Response to ketamine, assessed 24 hours after the fourth infusion, is defined as $\geq 30\%$ reduction in PTSD symptom severity on the CAPS-5, administered to the participant by a trained clinical rater, compared to baseline (prior to any infusions). This degree of improvement is commonly used in clinical trials in individuals with PTSD to represent clinically significant PTSD symptom improvement,⁶²⁻⁶⁴ and was also employed in our completed RCT of repeated ketamine for PTSD.⁸

d. WET Sessions:

WET consists of five sessions, with the first session lasting 1 hour and each subsequent session lasting approximately 40 minutes. The first session includes psychoeducation about common trauma reactions and the treatment rationale, presented by the therapist. The participant is then given general instructions for completing the trauma narratives and specific instructions for completing the first 30-minute narrative writing during that first WET session. All WET sessions begin with the therapist reading the specific writing instructions, clarifying any questions the participant might have, and leaving the instructions with the participant during the 30-minute writing session. Writing instructions begin with a focus on the details of the trauma and then shift to the meaning of the trauma event. After 30 minutes of writing, the therapist stops the writing and conducts a 5-10 minute check-in regarding how the writing session went for the participant.

All participants will be administered WET, beginning after they complete the first four infusions. WET will be delivered remotely by therapists to participants in their homes, via a HIPAA-compliant video telehealth platform, using methods implemented before the COVID-19 pandemic and further developed during the pandemic by study consultant [name], who co-developed the WET intervention.⁶⁵ Therapists will be Master's- or PhD-level mental health providers, supervised by [name]. WET will be delivered over a total of two weeks. The first two sessions of WET will be delivered starting after completion of the first four ketamine infusions, and interleaved with the last 2 ketamine infusions (each WET session and ketamine infusion occurring on one of four different days). The ketamine dose and administration protocol will be the same for all six infusions. The last three sessions of WET will be delivered the following week, after completion of the six ketamine infusions. Participant narratives will be collected as part of the WET sessions, as they are a necessary part of treatment and are used to ensure that the instructions for each writing session are followed by the participants. Collection will be completed securely, either by uploading a picture of the narratives to the REDCap database, uploading a scanned copy of the narratives, or by participants delivering the narratives in person (if there is a planned in-person visit shortly thereafter) or by mail.

e. Assessments and Outcome Measures (please see **3.1 Schedule of Activities** for additional details). Assessments will be administered weekly starting at baseline, prior to the first infusion.

Primary outcome measure: The Clinician-Administered PTSD Scale (CAPS-5),⁵⁰ the gold standard measure in clinical trials in individuals with PTSD, will be administered weekly by a blinded clinical rater. The primary outcome is change in PTSD symptom severity as measured by the CAPS between baseline and 12 weeks following the start of WET. All participants will be followed for 12 weeks. Participants who remain improved will additionally be followed monthly for 12 to 24 weeks.

Secondary outcome measures (exploratory): The CAPS-5 will be administered weekly (beginning at baseline prior to the first ketamine infusion) until 6 weeks from the start of WET; thereafter, the CAPS-5 will be administered weekly as tolerated until 12 weeks; all participants will be administered the CAPS-5 at the 12-week time point. Participants who maintain PTSD symptom improvement after 12 weeks will be assessed monthly up to 24 weeks from the start of WET or until loss of improvement, by the blinded clinical rater. The PCL-5 and SDS (self-report scales), the MADRS (administered by the blinded clinical rater), and the CGI-S and CGI-Improvement scales (administered by a study psychiatrist or clinician) will be administered at the same time points until 12 weeks, and then monthly up to 24 weeks or until loss of improvement (See **3.1 Schedule of Activities**). The Quick Inventory of Depressive Symptomatology-Self-Report version (QIDS-SR)⁶⁶ and the Impact of Events Scale-Revised (IES-R),⁶⁷ both self-report scales, will be administered at baseline, 24 hours after the first infusion, at each infusion visit, and on the day of response to ketamine assessment, to capture any ketamine-related rapid changes in symptom levels. An abbreviated version of the Medical Outcomes Study Social Support Survey (MOS-SSS),⁶⁸ the Centrality of Event Scale (CES),⁶⁹ and the Perceived Ability to Cope with Trauma Scale (PACT)⁷⁰ will be administered at baseline (prior to any infusions) and again 3 weeks after the first WET session; data from these scales will be used for Aim-3 analyses.

Safety Assessments: Participants will be evaluated prior to each infusion by the PI or another study-affiliated psychiatrist; including review of vital signs, weight/BMI, drug and pregnancy tests, concomitant medications and adverse events. Participants will be monitored continuously during all ketamine infusions. On infusion days, side effects will be assessed with the Patient-Rated Inventory of Side Effects (PRISE) Adverse Event Visit Checklist,⁷¹ the Clinician-Administered Dissociative States Scale (CADSS),⁷² the Brief Psychiatric Rating Scale (BPRS) 4 items assessing positive symptoms,⁷³ and the Young Mania Rating Scale first item.⁷⁴

f. Online Extinction Learning Task (see **Figure 7** : The computerized task, administered online, consists of three phases: an initial aversive conditioning phase (in context A), extinction learning phase (in context A), and further extinction learning (in novel context B) (see **Figure 6**). Importantly, the conditioned stimulus (CS) associated with the aversive loss outcome (US), the CS+, is only partially reinforced ($P(US|CS+)=1/3$), and the transition to extinction ($P(US|CS+)=0$) is unsignaled. This design maximizes uncertainty about whether CS+ trials during extinction should be grouped with unreinforced conditioning phase CS+ trials, implying a common cause is responsible for both kinds of observations, or instead that the change in contingencies indicates it is likely that a new cause is active in the environment. The predictive measure generated from this task for Aim 2 analyses is the *difference in discrimination between CS+ and CS-* across the first six blocks of the task. Further, loss expectancy ratings data from each trial of the online extinction task will be analyzed via a computational model of latent cause inference developed by Gershman, Niv, and colleagues^{75,76} (see **Data Analysis Strategy**). There are *two versions of the task* (see **Figure 7** note): one version will be administered prior to any ketamine infusions, and the second version

after completion of the first four infusions. We will examine whether ketamine-induced improvement in extinction learning is associated with improvement in PTSD symptoms from baseline to 12 weeks from start of WET.

4.2 SCIENTIFIC RATIONALE FOR STUDY DESIGN

Preliminary Data:

RCT of repeated IV ketamine for PTSD. Following our initial proof-of-concept RCT of single-dose IV ketamine infusion in patients with chronic PTSD,⁶ we completed the first RCT of repeated IV ketamine infusions in individuals with chronic PTSD (six infusions over two consecutive weeks), compared to repeated IV infusions of the psychoactive placebo midazolam (n=30). Participants' primary trauma ranged from assault to the WTC attacks/recovery work, and PTSD duration averaged 15 years. Results revealed a robust, large-magnitude improvement in PTSD symptom severity in the ketamine group from baseline to

[figure not shown]

Figure 3. Effect of Treatment with Ketamine (vs. Midazolam) on PTSD Symptom Severity⁽¹⁰⁾

[figure not shown]

Figure 4. Risk of Loss of Response among Responders to Ketamine and Midazolam Infusions in PTSD⁽¹⁰⁾

week 2, compared to the midazolam group, assessed with the CAPS-5 ($F=5.97$, $df=2$, 55, $p=0.0045$, $d=1.13$).⁸ In the ketamine group, the CAPS-5 total score was 11.88 (SE=3.96, $p=0.004$) points lower ($d=1.13$, 95% CI=0.36-1.91; see **Figure 3**); 67% of participants were treatment responders, defined as $\geq 30\%$ improvement from baseline on the CAPS-5, compared with 20% in the midazolam group ($\chi^2=4.89$, $p=0.03$).⁸ Ketamine infusions were additionally associated with significantly greater improvement in comorbid depressive symptoms from baseline to 2 weeks, assessed with the Montgomery-Åsberg Depression Rating Scale (MADRS; $F=5.68$, $df=2$, 55, $p=0.006$, $d=0.92$), and on a global measure of clinical improvement, the Clinical Global Impression Severity Scale (CGI-S; $F=5.19$, $df=2$, 50, $p=0.009$). In participants who responded to ketamine, median time to loss of response was 27.5 days after the 2-week primary outcome assessment day (see **Figure 4**), motivating the proposed study, investigating a novel approach aimed at maintaining symptom improvement over time by adding a brief and scalable exposure-based psychotherapy to a course of ketamine infusions delivered with the same schedule of six infusions over two consecutive weeks, which was associated with rapid and robust symptom improvement in individuals with chronic PTSD in our completed RCT.⁸

Development of Written Exposure Therapy. In NIMH-funded studies, Co-Investigator [name] and colleagues have demonstrated the efficacy of WET in reducing PTSD symptom severity,³⁹⁻⁴¹ including an NIMH-funded RCT (R01MH095737) that demonstrated WET's non-inferiority to CPT,⁴¹ one of the two therapies with highest evidence base for the treatment of PTSD (see **Figure 5**). Of key relevance to the proposed RCT, greater physiological activation in response to written exposure during the first session was found to significantly predict symptom improvement from WET, suggesting that fear extinction learning is a mechanism underlying improvement in PTSD with WET.^{34,35} If ketamine infusions in

individuals with chronic PTSD enhance extinction learning, a mechanism thought to underlie WET, the addition of WET might result in enhanced PTSD symptom improvement through a synergistic effect.

Online Extinction Learning Task: Study in WTC Workers and Survivors with and without PTSD. Our research team developed the online Extinction Learning Task proposed for Aim 2 of this study, led by postdoctoral fellow [name].⁴⁸ This behavioral extinction learning paradigm consists of three phases: (1) initial aversive conditioning phase, in context A; (2) extinction learning phase, also in context A; and (3) further extinction learning, in new context B (see **Figure 6**). Participants are told that they are traveling through different zones of a spaceship. In order to power their trip home, they need to escape with enough space coins. These coins are carried by helper robots, but some are unreliable. Participants are asked to rate (sliding bar), on each trial, how likely they think that particular robot would be to lose the coins it is carrying. **Task sensitivity to PTSD status:** Pilot data were collected for $N=48$ adults with DSM-5 criterion A trauma exposure to the World Trade Center (WTC) disaster (WTC responders and survivors; mean age 53 ± 7.0 , $N=16$ female). $N=34$ (71%) participants currently met DSM-5 criteria for WTC-related PTSD (mean PCL-5 total score 44.1 ± 8.6), and $N=14$ (29%) participants were highly resilient to WTC-related exposures (no current or lifetime diagnosis of PTSD or other DSM-5 Axis-I disorder; mean PCL-5

[figure not shown]

Figure 6. Loss expectancy ratings on the extinction task by conditioned stimulus (CS) type and task stage, by clinical group (PTSD, Resilient). Data is represented separately for WTC-exposed individuals who met criteria for WTC-related PTSD ($N=34$), and resilient individuals who were exposed to criterion A trauma during the WTC disaster but never met diagnostic criteria for PTSD ($N=14$). Error bars represent standard error of the mean. CS+,

total score 1.6 ± 1.7). An earlier version of the online Extinction Learning Task that we propose to use in this study was administered to all participants. Behavior on the Extinction Learning Task differed between the PTSD and Resilient groups (repeated-measures ANOVA of loss-expectancy ratings with within-subjects factors of conditioned stimulus [CS] type, task stage, and clinical group, using Tukey-LSD correction for multiple comparisons in follow-up contrasts). Specifically, there was a significant CS x group interaction ($F_{1,806}=12.6$, $p<0.001$) –driven by a tendency towards higher overall loss prediction ratings for CS- stimuli (less discrimination between CS+ and CS- stimuli) in symptomatic individuals (mean difference in CS- rating PTSD vs resilient 13.8 [SE 5.7], 95%CI -1.3–28.9, $p=0.08$; difference in CS+ rating PTSD vs resilient 2.1 [SE 5.7], $p>0.9$). Discrimination between CS+ and CS- stimuli across the first six blocks of the task differed between the groups [$t_{34}=-2.02$, $p=0.051$, mean discrimination (difference in loss expectancy ratings) in the PTSD group=20.1, in the Resilient group=35.6 (points on a scale 0-100), Cohen's $d = 0.57$. Computational latent cause modeling in this study showed that higher PTSD symptom severity, and specifically higher

severity of intrusion symptoms, was associated with the belief that the same underlying cause explains events observed during conditioning and extinction stages of the task.⁴⁸

For Aim 2, extinction learning will be measured twice, with two versions of the online Extinction Learning Task: (1) before the first ketamine infusion and (2) after completion of four ketamine infusions (pre-WET). Extinction learning will be defined as the difference in discrimination between the aversively conditioned (CS+) and safe (CS-) stimuli on the first six blocks of this task. Ketamine-induced change in extinction learning will be evaluated as a predictor PTSD symptom improvement from baseline to 12 weeks from the start of WET. A recently developed computational model^{75,76} will be employed to determine whether differences in discrimination between CS+ and CS- are related to differential inferences about the causal structure of the task during learning (i.e., participants' belief that one vs. multiple underlying causes explain observations during progression through the task).⁴⁸

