9 STATISTICAL CONSIDERATIONS

9.1 STATISTICAL HYPOTHESES

- Primary Efficacy Endpoint(s):
 - The primary outcome is change in PTSD symptom severity from baseline to 12 weeks from the start of WET measured by the Clinician-Administered PTSD Scale for DSM-5 (CAPS-5) score at 12 weeks from the start of WET minus the CAPS-5 score at baseline. The analysis of the primary endpoint for this pilot study will be descriptive and no formal hypothesis testing will be conducted. The mean change in CAPS-5 score and corresponding 95% confidence interval will be reported.

- Secondary Efficacy Endpoint(s) (Exploratory):

In this early-phase study, analyses of secondary efficacy outcomes will be considered exploratory and hypothesis-generating. Therefore, no formal hypothesis testing will be conducted.

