9.4.2 ANALYSIS OF THE PRIMARY EFFICACY ENDPOINT(S)

The primary outcome is change in PTSD symptom severity from baseline to 12 weeks from the start of WET measured by the Clinician-Administered PTSD Scale for DSM-5 (CAPS-5) score at 12 weeks from the start of WET minus the CAPS-5 score at baseline. The analysis of the primary endpoint for this pilot study will be descriptive. The mean change in CAPS-5 score from baseline with corresponding 95% confidence interval will be reported.

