The relationship between depressive symptoms and PTSD will be explored to assess whether worsening depressive symptoms correlate with worsening PTSD symptoms and whether there is any evidence that the worsening of one precedes the other. Scale scores of both measures will be plotted over time together to evaluate trends descriptively. Fixed and mixed effects regression models will also be explored to estimate effects and 95% confidence intervals.

- Finally, additional analyses might explore differences with a historical comparison group from our published repeated IV ketamine study for PTSD (Feder et al 2021).

Aim 2 (Exploratory): To evaluate whether ketamine-induced change in extinction learning predicts maintenance of ketamine response over time. We will use regression models to evaluate whether ketamine-induced change in extinction learning [improvement in extinction learning between two time points: (1) before infusions and (2) after four infusions (prior to starting WET), measured with the computerized online Extinction Learning Task, is associated with change in CAPS-5 at 12 weeks after the start of WET. A univariable model of ketamine-induced change on the extinction learning measure [discrimination between aversively conditioned (CS+) and safe (CS-) stimuli over the first six blocks of the task] and changes in CAPS-5 score will be examined. Beta coefficients and 95% confidence intervals will be reported. A significant association between greater ketamine-induced improvement in extinction learning and improvement in CAPS-5 scores will be considered supportive of Hypothesis 2.

Computational analyses: Loss expectancy ratings data from each trial of the online extinction task will be analyzed via a computational model of latent cause inference developed by Gershman, Niv, and colleagues.^{75,76} Importantly, this model has previously been shown to be able to explain individual differences in failure of extinction learning in both healthy volunteers and trauma-exposed individuals

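### The Aim 2 regression of CAPS-5 change on task change leaves out baseline CAPS-5, so its slope could be partly confounded by starting severity; an adjusted slope should be shown beside it

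*Combined protocol and SAP*

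**What the plan says.** Section 4.2 names the predictor and the outcome window: "Ketamine-induced change in extinction learning will be evaluated as a predictor PTSD symptom improvement from baseline to 12 weeks". The model is in section 9.4.3, under Aim 2. The question there is whether task change "is associated with change in CAPS-5 at 12 weeks after the start of WET", and the analysis is "A univariable model of ketamine-induced change on the extinction learning measure" against change in CAPS-5. Section 9.4.2 defines CAPS-5 change as a raw difference: "score at 12 weeks from the start of WET minus the CAPS-5 score at baseline".

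For reporting, section 9.4.3 says "Beta coefficients and 95% confidence intervals will be reported". It then adds a rule: "A significant association between greater ketamine-induced improvement in extinction learning and improvement in CAPS-5 scores will be considered supportive of Hypothesis 2". No section adds baseline CAPS-5 or any other covariate to this model. The schedule of activities (section 1.3) has the CAPS-5 on Day 1, before the first infusion.

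Sections 9.4.3 and 9.4.9 label Aim 2 exploratory. Section 9.1 says of the secondary efficacy outcomes: "Therefore, no formal hypothesis testing will be conducted".

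**The concern.** A raw change score contains the baseline value. Unless baseline and week 12 are very strongly correlated, patients who start higher tend to fall further. If those patients also tend to gain more on the task, the two changes will be correlated even when task gain tells us nothing further about outcome.

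The sponsor's pilot makes the second link conceivable. Section 4.2 reports "less discrimination between CS+ and CS- stimuli) in symptomatic individuals", so more severe patients might have more room to improve on the task. Both links would push the slope in the direction that section 9.4.3 would read as supportive. At stake are the reported beta, which a follow-on study might use, and the claim of support for Hypothesis 2.

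**Working it through.** **The plan's own figure.** There is none for Aim 2. The only precision statement (section 9.2) is a 95% half-width of 0.5 SD for the mean CAPS-5 change with 15 patients. It reproduces with the normal quantile: 1.96/√15 = 0.506. It does not bear on the Aim 2 slope.

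**What significance requires.** With n = 15 and two-sided 0.05 (assumed, to match the 95% interval), t(0.975, 13) = 2.160. The critical correlation is 2.160/√(2.160² + 13) = 0.514.

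**Link 1: starting severity and CAPS-5 improvement.** The documents give no value. For baseline SD s_b, week-12 SD s_w and baseline to week-12 correlation ρ, the correlation of baseline with improvement is (s_b − ρ·s_w)/√(s_b² + s_w² − 2ρ·s_b·s_w). I assume s_w = 10.5. No week-12 SD is stated; 10.5 is back-calculated from the week-2 ketamine versus midazolam contrast in section 4.2, 11.88/1.13. I also assume s_b = 8 or 10.5 and ρ = 0.3 or 0.5.
- Lowest (s_b = 8, ρ = 0.5): 2.75/9.5 = 0.29.
- Highest (s_b = 10.5, ρ = 0.3): 7.35/12.42 = 0.59.

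The rows for 0.3 and 0.5 below are the central cases. 0.7 is an outer bound: with equal SDs it needs ρ close to zero.

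**Link 2: starting severity and task gain.** Again no value is given. A rough calibration from the pilot in section 4.2:
- Group difference in discrimination: 35.6 − 20.1 = 15.5. With d = 0.57 the implied SD is 15.5/0.57 = 27.2.
- Slope per PCL-5 point: 15.5/(44.1 − 1.6) = 0.365.
- Implied correlation within PTSD (PCL-5 SD 8.6): 0.365 × 8.6/27.2 = 0.115.
- If performance after the infusions is unrelated to severity, and the two administrations have equal SDs and correlation ρ_T, the correlation of severity with gain is 0.115/√(2(1 − ρ_T)). This is 0.10, 0.12 and 0.15 for ρ_T = 0.3, 0.5 and 0.7.

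**False-positive rate from severity alone.** Simulation, n = 15, 100,000 trials per cell; task gain and CAPS-5 improvement are independent given baseline. The correlation induced is the product of the two links. Each cell shows the two-sided rate, with the rate in the supportive direction (nominal 2.5%) in brackets.

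| Severity with CAPS-5 improvement | Severity with gain 0 | 0.12 | 0.15 | 0.3 | 0.5 |
|---|---|---|---|---|---|
| 0.3 | 5.0% (2.5%) | 5.2% (3.4%) | 5.2% (3.5%) | 6.1% (5.0%) | 8.4% (7.6%) |
| 0.5 | 5.1% (2.5%) | 5.5% (4.0%) | 5.8% (4.4%) | 8.3% (7.6%) | 14.7% (14.5%) |
| 0.7 | 5.1% (2.6%) | 5.9% (4.7%) | 6.7% (5.7%) | 11.4% (11.1%) | 25.3% (25.3%) |

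With baseline CAPS-5 in the model, the two-sided rate is 4.9% to 5.2% throughout. The 8% to 19% range comes from the s_b, s_w, ρ grid above with a severity–gain correlation of 0.5.

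**Size of the spurious slope.** Per SD of task gain it is r(severity, gain) × (s_b − ρ·s_w). At 0.10 to 0.15 this runs from 0.10 × 2.75 = 0.3 to 0.15 × 7.35 = 1.1 CAPS-5 points. At 0.5 it reaches 0.5 × 7.35 = 3.7. For scale, the 95% half-width of the univariable slope is about 2.160 × SD of change/√13, or 5.7 to 7.4 points for change SDs of 9.5 to 12.42.

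**Precision after adjustment.** Residual degrees of freedom go from 13 to 12. Across the same grid the ratio of mean interval widths (adjusted to univariable) is 0.85 to 1.17. It is lowest when gain is unrelated to severity and highest when their correlation is 0.5.

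**The case against.** The confounding needs severity to be related to task gain, not only to task performance. The pilot compared people with PTSD with highly resilient people on an earlier version of the task, and the discrimination contrast had p = 0.051. It reports no gradient of discrimination with severity within PTSD and nothing about change after ketamine. All participants here have PTSD with CAPS-5 of at least 30, which narrows the range of severity. More severe patients could equally gain less. This stands, and it is why the size is set by the scaled pilot figures.

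Adjustment is also not a guaranteed cure. The simulation above assumes that observed baseline CAPS-5 carries all the confounding. If instead true change is unrelated to severity and baseline CAPS-5 is measured with error (assumed reliability 0.6 to 0.8), the univariable model holds 5% and the adjusted one gives 5% to 8% two-sided. That excess goes against the hypothesis: the false-supportive rate is about 0.8% to 2.4%. This supports showing both slopes rather than replacing one with the other. Baseline task discrimination would also remain outside the model, which is a real limit.

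Finally, Aim 2 is exploratory and section 9.1 disclaims formal testing of secondary outcomes. That lowers the stakes. It does not remove the point, because section 9.4.3 still reports a beta and attaches a significance rule to it.

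**Conclusion.** The omission is real and cheap to repair, but its likely effect is small. At correlations scaled from the pilot (0.10 to 0.15), the two-sided false-positive rate is about 5% to 7%. The false-supportive rate is about 3.5% to 5% against 2.5%, reaching 5.7% only in the outermost cell. The spurious slope is well inside the interval's half-width. I rate this as a point to consider.

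A reader might infer that starting severity alone is likely to produce the significant association, with error rates of 8% to 19%. The documents do not support that. Those rates need a severity–gain correlation of 0.5, which nothing in them indicates; at zero the rate stays at 5%.

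The conclusion rests on these assumptions: the two correlations; the SD of 10.5, which comes from a week-2 contrast; a linear scaling across two extreme pilot groups; and a two-sided 0.05 threshold. It also takes Day 1 as the starting point for CAPS-5 change, as sections 4.2 and 9.4.2 do, although the general rule in section 9.4.1 computes change from the pre-WET day.

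**What to change.** In section 9.4.3, Aim 2, add a second model: week-12 CAPS-5 regressed on change in task discrimination, with Day 1 CAPS-5 as covariate. Report its slope and 95% confidence interval side by side with the univariable slope. State that Hypothesis 2 is called supported only if the association holds after adjustment. With Day 1 CAPS-5 in the model, the task slope is the same whether the outcome is the week-12 score or the change (week 12 minus Day 1), so the endpoint does not change.

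The cost is a sentence or two and one degree of freedom, with no new data. The interval may be up to about 17% wider if task gain and severity are strongly correlated, and up to 15% narrower if they are unrelated. If baseline CAPS-5 is measured with error, the adjusted slope may be pulled somewhat against the hypothesis; the univariable slope beside it lets the reader judge.
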